1.0 Background

Diabetes is a leading cause of cardiovascular disease, renal failure, vision loss and non-traumatic lower limb amputations. Diabetes self-management can prevent or delay diabetes-related complications, yet patients struggle to consistently engage in recommended self-care behaviors. Patients with diabetes may lack the understanding and motivation necessary to successfully manage their disease. Among patients with diabetes, studies have found that higher patient activation (i.e., knowledge, skills and confidence to manage their own health and care) is associated with healthy eating, blood sugars monitoring, eye exams and immunizations. Many of these findings were reported in diverse and disadvantaged populations.

Patient portals offer a vehicle for interventions aimed at increasing patient activation, improving understanding, and promoting self-management, while overcoming the limitations of costly and difficult to scale face-to-face programs. We recently applied user-centered design sprint methodology and key strategies for patient engagement to develop a multi-faceted patient portal intervention, My Diabetes Care (MDC), designed to help patients better understand their diabetes health data as well as support self-management. MDC was embedded within an established patient portal, My Health at Vanderbilt (MHAV), on Epic's MyChart platform and best viewed on desktop devices. MDC uses infographics to visualize and summarize patients' diabetes health data, incorporates motivational strategies (e.g., social comparisons), and provides literacy-level appropriate educational resources. MDC is grounded in a well-established Chronic Care Model (CCM) adapted for eHealth (i.e., healthcare practices supported by electronic processes and communication). By leveraging elements within the Model's five domains (self-management support, delivery system design, decision support, clinical information systems, and eHealth education), MDC has the potential to create more informed and activated patients leading to improved outcomes.

In a prior longitudinal study of the MDC, participants, including those with limited HL, highly rated its usability, anticipated continued use, and reported that it improved their understanding of their personal diabetes health data. In addition, participants' patient activation scores significantly increased over the study period. When asked to identify enhancement that would increase their satisfaction with MDC participants indicated a desire use MDC on mobile devices. Moreover, most patient portal users now access the portal via mobile devices. Thus, we designed and assessed task-based usability of a mobile-friendly version of MDC. We found the final prototype of MDC Mobile (MDC-m) was very satisfying for participants to use.

2.0 Rationale and Specific Aims

To assess usage patterns, user experience, and to uncover errors in functionality prior to larger interventional trials, we will conduct a longitudinal usability study MDC-m. The study will utilize questionnaires to quantify participants' perceptions and responses to the MDC-m and semi-structured interviews to comprehensively assess users' experience, barriers to use, and reasons for non-use or discontinued use. Combining qualitative and quantitative assessments of usability identifies more usability concerns than quantitative (e.g., questionnaires) assessments alone. Each participant will have access to the MDC-m for 1 month from the time of enrollment. This duration allows sufficient time for participants to become familiar with MDC-m and determine if and how to use MDC-m in the management of their diabetes.

In the current study, we aim to: (1) assess the feasibility of the intervention and (2) the usability of the MDC-m over time among a diverse group of patients with type 2 diabetes mellitus (T2DM).

3.0 Inclusion/Exclusion Criteria

Participants will be eligible for the study if they have T2DM, currently taking at least one medication for diabetes, are able to speak and read in English, are age 21 or over, have reliable access to a smartphone or tablet with internet access and have a MHAV account.

We will exclude patients living in long term care facilities, patients with known cognitive deficits, patients with severe visual or hearing impairment, patients with unintelligible speech (e.g., dysarthria), and patients currently participating in other diabetes related studies.

4.0 Enrollment/Randomization

Participants will be able to complete an electronic consent form and enroll online via Research Electronic Data Capture (REDCap™) version 5.0.8.

5.0 Study Procedures

Setting. The Vanderbilt Adult Primary Care (VAPC) clinics are located throughout the greater Nashville, TN area. An EHR (Epic Systems Corp.) stores all clinical data and patients receive access to their clinical data via an integrated and highly-adopted patient web portal, My Health at Vanderbilt (MHAV), that is accessible on desktops and via a native mobile app for iOS and Android mobile operating systems.

Participants and Recruitment. Potential participants will be identified automatically using VUMC's *Subject Locator* to query the EHR for patients with upcoming clinic appointments who meet the discrete inclusion and exclusion criteria. In addition, VUMC population health and quality improvement initiatives have created a report that identifies established patients with diabetes who receive care at the primary care clinics participating in the study. These patients are the target population for study (i.e., Vanderbilt primary care patients with diabetes) and as such these patients are potentially eligible to participate in the study. With permission of the clinic director, potentially eligible patients, will be mailed a recruitment letter describing the study and providing contact information for IRB approved study personnel. If after a receiving the letter, a patient is interested in the study, the patient may contact study personnel to learn more and consider participating in the study. The recruitment letter will include a QR code and URL link to the eligibility screener in Research Electronic Data Capture (REDCap). Participants whose REDCap screener indicates they are eligible can advance to the REDCap ICD. Participants will complete an electronic consent form and enroll online via REDCap. Our target enrollment is 65 participants. In accordance with best practices and to reflect a range of patient experience with diabetes and groups with distinct usability needs, we will aim to recruit a study sample with at least 25% representation of each of the following characteristics: (a) limited health literacy and (b) age 65 or over. Some participants may have one or more of these characteristics.

Data Collection and Outcome Measures. Study participants will complete questionnaires electronically via email using REDCap at two time points: enrollment (T_0) and end of study (T_1). Participants will complete an enrollment questionnaire (T_0) including basic sociodemographic questions and validated measures of health literacy and eHealth literacy.

The primary outcome measures (**Table 1**) will be: (a) ease of use and satisfaction as assessed by the System Usability Scale at T_1 , (b) system usage data of MDC-m at T_1 , (c) user experience as assessed by end of study questionnaire and semi-structured interviews at T_1 . In addition, we will assess pre/post change in the following secondary cognitive and behavioral outcomes (Table 1) to estimate effect size and standard deviations for power analyses necessary to plan subsequent randomized controlled trials.

Table 1. Outcome Measures

Primary Outcomes	Measures	Variable Type	How Collected	Time Point
Usability	System Usability Scale	Continuous	Questionnaire	T_1
System usage data	MDC-m visits Duration of MDC-m visits	Continuous and categorical	Self-report	T_1
User experience	Assess participants' perspectives on content, layout, acceptance, and particular features and functionality	Categorical, Qualitative	Questionnaire, Interviews	T_1
Secondary Cognitive/Behavioral Outcomes				
Diabetes knowledge	Short Diabetes Knowledge Instrument (SDKI)	Continuous	Questionnaire	T_0 and T_1
Diet adherence	Summary of Diabetes Self-Care Activities (SDSCA) – General Diet Subscale Summary of Diabetes Self-Care Activities (SDSCA) – Specific Diet Subscale	Continuous	Questionnaire	T_0 and T_1
Exercise adherence	SDSCA – Exercise Subscale	Continuous	Questionnaire	T_0 and T_1
Medication adherence	Adherence to Refills and Medications Scale	Continuous	Questionnaire	T_0 and T_1
Glucose self-monitoring adherence	SDSCA – Self-monitoring of Blood Glucose Subscale	Continuous	Questionnaire	T_0 and T_1
Medication adherence	Adherence to Refills and Medications Scale (ARMS)	Continuous	Questionnaire	T_0 and T_1
Diabetes self-efficacy	Perceived Diabetes Self-Management Scale (PDSMS)	Continuous	Questionnaire	T_0 and T_1
Diabetes distress	Problem Areas in Diabetes Scale (PAID)-5	Continuous	Questionnaire	T_0 and T_1
Knowledge of Diabetes Measures	Unique study specific items to assess participants' knowledge of measures of diabetes health status	Categorical	Questionnaire	T_0 and T_1
Diabetes Attitudes	Unique study specific items to assess participants' attitudes toward social and goal-based comparison information regarding their diabetes health status	Categorical	Questionnaire	T_0 and T_1

Diabetes Readiness for Change	Four items assessment resources to assess stage of change based on the Transtheoretical Model (TTM) of behavior change. It includes questions on physical activity, medication management, glucose self-monitoring, and diet.	Categorical	Questionnaire	T ₀ and T ₁
-------------------------------	---	-------------	---------------	-----------------------------------

Based on pilot testing, we estimate time to completion for questionnaires to be 20 minutes at T₀ and 25 minutes at T₁. Participants will be compensated \$40 for completing the enrollment questionnaire, \$35 for completing the study end questionnaire, and \$5 for first 10 minutes of MDC-m use during which participants will be encouraged to familiarize themselves with the full functionality of the MDC-m.

At the conclusion of their one month of MDC-m access, we will conduct one-on-one, semi-structured interviews with a subsample of at least 10 participants including at least two participants from each of the purposively sampled groups (i.e., participants with limited health literacy and age 65 or over). This methodology is most appropriate for in-depth assessment of patients' perceptions and reactions regarding a proposed intervention. Interviews are preferred over focus groups for understanding usability because focus groups can amplify bias and individual opinions. Interviews will take place by phone or via Zoom within two weeks of participants concluding their one month of MDC-m access and will last approximately 30-40 minutes. Participant MDC-m access will be available during the interview to allow participants to recall and/or reference particular concerns or perceptions of usability. A trained interviewer will use a semi-structured interview guide to facilitate the interview and elicit in-depth understanding of participants' perceptions and experiences with specific MDC-m functionality as well as barriers to use, and reasons for non-use or discontinued use. Additional participants will be enrolled until saturation is reached. Saturation will be defined as no new usability concerns raised in the preceding two interviews and typically occurs between 10 and 30 interviews. Participants will be compensated an additional \$40 for the interview.

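### System usage, listed as a primary outcome measure, is collected only by self-report at T1, so it rests on recall over the access month and is absent for anyone who does not return T1

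*Combined protocol and SAP*

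**What the plan says.** Section 2.0 opens the rationale with "To assess usage patterns, user experience, and to uncover errors in functionality prior to larger interventional trials", and the first of its two aims is feasibility. On exposure it says: "Each participant will have access to the MDC-m for 1 month from the time of enrollment".

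Section 5.0 (Data Collection and Outcome Measures) lists three primary outcome measures. The second is "b) system usage data of MDC-m at T_1". The usage row of Table 1 gives the measures as "MDC-m visits Duration of MDC-m visits", the mode of collection as self-report, and the time point as T1. It is the only row in the table with that mode of collection. Questionnaires are completed "at two time points: enrollment (T_0) and end of study (T_1").

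Section 6.0 names the SUS score at T1 as the primary outcome. For usage it offers only the general commitment to descriptive statistics. It gives no usage-specific analysis and no rule for missing T1 data.

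**The concern.** The label promises system data, but the collection method delivers participants' recollection. Two things follow from the design.

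- **Recall.** A report at T1 of how many visits were made, and how long they lasted, has to look back over the month. The plan describes no diary, interim contact, usage instrument or recall window. Retrospective answers are a poor source for when visits happened or when someone stopped, which is what a study of usage patterns needs.
- **Missing values.** T1 self-report is the only named source of usage, so a participant who does not return T1 has none. The study wants to understand people who never used the tool or gave it up, and they may well be over-represented among those who do not return.

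The study is meant to prepare for larger trials. An uptake figure that describes only T1 responders, but is reported as system usage, could carry into their planning.

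**Working it through.** The plan gives no usage figure, expected T1 return rate or derivation of the sample size, so there is nothing to reproduce. The check is a comparison of the text followed by an illustration.

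**Text.** One month of access (Section 2.0), questionnaires at enrolment and end of study only (Section 5.0) and usage by self-report at T1 (Table 1) together mean recall over the access month, among T1 responders. No section describes portal logs, audit data or other automatic capture. The interviews in Section 5.0 cover a subsample of at least 10. They explore perceptions and reasons for non-use and do not quantify use across the sample.

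**Illustration: bounds on the proportion who used MDC-m.**

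Inputs:
- N = 65, from Section 5.0: "Our target enrollment is 65 participants".
- m = number not returning T1, at 5%, 10%, 20% and 30% of 65, rounded (assumed).
- x = number of responders reporting any use, set at about 90% of responders (assumed) and taken at face value.

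Formulas:
- Observed proportion = x/(N − m).
- Lower bound, all non-returners non-users = x/N.
- Upper bound, all non-returners users = (x + m)/N.
- Width = m/N.

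| Missing m | Observed | Lower | Upper | Width (points) | Observed minus lower (points) |
|---|---|---|---|---|---|
| 3 (5%) | 56/62 = 90.3% | 56/65 = 86.2% | 59/65 = 90.8% | 4.6 | 4.2 |
| 6 (10%) | 53/59 = 89.8% | 53/65 = 81.5% | 59/65 = 90.8% | 9.2 | 8.3 |
| 13 (20%) | 47/52 = 90.4% | 47/65 = 72.3% | 60/65 = 92.3% | 20.0 | 18.1 |
| 20 (30%) | 40/45 = 88.9% | 40/65 = 61.5% | 60/65 = 92.3% | 30.8 | 27.4 |

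The width depends only on m/N, not on the assumed level of use. With about 70% of responders reporting use and 13 missing, the observed figure is 36/52 = 69.2% and the bounds are 36/65 = 55.4% and 49/65 = 75.4%, again 20 points apart.

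At 90% reported use the interval lies mostly below the observed figure, so the largest possible error is overstatement. Whether the truth is near the lower bound depends on who fails to return T1, which the documents do not tell us. Recall error comes on top and cannot be sized from the documents.

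**The case against.** The strongest reply is that little rests on usage. Section 6.0 names SUS alone as primary, no test or decision rule uses the usage data, and this is a small study done ahead of larger trials. That stands, and it limits the weight of the point. It does not remove it: Section 5.0 and Table 1 still class usage as primary, and usage patterns are the first purpose stated in Section 2.0.

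Second, the interviews are assigned the reasons for non-use and discontinued use, and nothing makes them conditional on returning T1. This mitigates the gap, but a subsample of at least 10 cannot give the proportion who used the tool.

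Third, logs may not exist. The portal statement in Section 1.0 ("embedded within an established patient portal, My Health at Vanderbilt (MHAV), on Epic's MyChart platform") describes the parent tool, MDC, and not MDC-m. Section 3.0 requires a portal account, and MDC-m is the mobile-friendly version of that tool, so logging is plausible. It is not stated, and the fix needs a fallback.

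Fourth, the row may be no more than a wording slip. The documents cannot settle that, and either way the entry needs correcting.

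A reader might infer three stronger points that the documents do not support:

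- **That uptake will be overstated.** This requires non-users to return T1 less often. The plan gives no return rate and no link between return and use, it pays for the T1 questionnaire with no stated condition of use, and recalled counts can err downward.
- **That the payment "for first 10 minutes of MDC-m use" rewards reporting use, or shows that electronic records are already held.** The plan does not say how that use is confirmed, other arrangements are possible, and the payment does not extend to later visits.
- **That recall error will weaken a correlation between usage and SUS.** No such analysis is planned. Error shared between two self-reports could also raise a correlation instead of lowering it.

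**Conclusion.** The point holds. Followed as written, the plan yields recalled use among T1 responders under the label of system usage data. That it is self-report at T1 is explicit in Table 1. That it is recall over the month, and that it is missing for non-returners, are inferences from the timetable and from the absence of any other named source.

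The uncertainty in the proportion using MDC-m equals the share missing at T1: about 5, 9, 20 and 31 points at 5%, 10%, 20% and 30% missing of 65, all assumed rates. Overstatement is likely if non-users are less likely to return T1, and that condition is an assumption. No planned test is affected. The consequence is for the descriptive account of usage and feasibility and for what later trials take from it. This is a worthwhile, inexpensive improvement and not a flaw that undermines the SUS analysis.

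**What to change.** 1. In the usage row of Table 1, replace self-report with portal or MDC-m access logs for visits and their duration, taken for every enrolled participant over the access month. Stop the extract at the end of that month, because Section 5.0 also makes access available during the later interviews. Keep the self-report items as supportive.
2. If MDC-m access cannot be logged, rename the outcome *self-reported use among T1 responders*, report the T1 return rate, and show the proportion using MDC-m with a lower bound that counts non-returners as non-users. State the items and the recall period.
3. Reconcile Sections 5.0 and 6.0 on whether usage is primary or only SUS is.

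The cost of the first change is a table edit and a data request to the portal team, best settled before enrolment in case log capture cannot be recovered afterwards. Its drawback is that logged minutes may include idle time. The fallback costs only wording and one extra line of results.

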6.0 Statistical Analysis Plan

We will use descriptive statistics to characterize the study participants and survey data. We will use a one sample t-test to compare the mean SUS score at T1 to the threshold score of 71 indicative of "good" usability. To assess whether there was a significant improvement in the continuous secondary cognitive/behavioral outcomes from baseline to end of study (T₀ to T₁), we will perform two-sided paired t-tests on the pairwise differences. If any of the distributions of pairwise differences suggest asymmetry or nonnormality, the non-parametric Wilcoxon signed-rank test will be performed in lieu of paired t-tests. We will use the McNemar's test for to compare paired proportions. Our primary outcome will be System Usability Scale (SUS) score at the end of the study period (T1).

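### The effect size for later randomized trials is to come from uncontrolled pre/post change in a single group, which cannot estimate a between-arm effect

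*Combined protocol and SAP*

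**What the plan says.** The study has one group. Section 2.0 states: "Each participant will have access to the MDC-m for 1 month from the time of enrollment". Section 4.0 carries the word randomization in its title, but its text covers only online consent and enrolment: "Participants will be able to complete an electronic consent form and enroll online via Research Electronic Data Capture". On size, Section 5.0 says: "Our target enrollment is 65 participants". No effect size, SD, alpha, power or dropout allowance goes with that figure.

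Section 5.0 (Data Collection and Outcome Measures) gives the purpose of the pre/post secondary outcomes: "to estimate effect size and standard deviations for power analyses necessary to plan subsequent randomized controlled trials". Table 1 lists them. All are questionnaire measures taken at T0 and again at T1.

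Section 6.0 sets the analysis of the continuous ones: "To assess whether there was a significant improvement in the continuous secondary cognitive/behavioral outcomes from baseline to end of study", "we will perform two-sided paired t-tests on the pairwise differences", with a Wilcoxon signed-rank test as fallback. Neither section mentions a control, a discount, a confidence interval for the change, or a caution about carrying the change over to a randomized setting.

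**The concern.** A two-arm trial is powered on the difference between arms. A single-arm change is the sum of whatever MDC-m does and whatever would have happened anyway. Only the first part survives randomization, because the second appears in both arms and cancels.

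Three features of this plan could produce change without MDC-m:

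- The same knowledge and self-care questions are asked twice, about a month apart.
- Participants are under ordinary primary care throughout.
- Every secondary outcome is self-reported by people who know they have the tool.

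The plan has no means of separating these from an MDC-m effect.

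Randomized-trial planning is the only purpose that Section 5.0 gives for assessing change in these outcomes. Half of that purpose, the standard deviations, can be met here. The other half, the effect size, cannot. If the observed change is entered in a sample-size formula as though it were a between-arm difference, the later trial may be the wrong size, and nothing in this study's data would reveal it.

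**Working it through.** **What can be reproduced.** The only stated figure is 65 enrolled. It comes without inputs, so it cannot be re-derived. The documents also give no figure for any later trial. Everything below is therefore an illustration.

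**Assumed inputs (none in the documents).** Observed standardized change d = 0.40; later trial with 1:1 allocation, two-sided alpha 0.05 and 80% power; a share s of the observed change would also occur in controls. The true between-arm effect is then d(1 − s). A negative s means that controls worsen.

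**Step 1: size of a trial planned on the full change.** By the normal approximation, n per arm = 2(1.96 + 0.8416)²/d² = 2 × 7.849/0.16 = 98.1, so 99. The two-sample t-test calculation gives 100, which is used below.

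**Step 2: power of that trial when part of the change is shared.** Power ≈ Φ(d(1 − s)·√(n/2) − 1.96), with √(100/2) = 7.071. For s = 20%: 0.32 × 7.071 − 1.96 = 0.303, and Φ(0.303) = 0.62. The t-test calculation gives 0.615. The table uses the t-test.

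| Share s also seen in controls | True between-arm effect | Power at 100 per arm | Per arm needed for 80% |
|---|---|---|---|
| 0% | 0.40 | 80% | 100 |
| 10% | 0.36 | 72% | 123 |
| 20% | 0.32 | 61% | 155 |
| 30% | 0.28 | 50% | 202 |
| 50% | 0.20 | 29% | 394 |
| −20% (controls worsen) | 0.48 | 92% | 70 |

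The loss depends on s and hardly at all on the starting d. For d from 0.2 to 0.5, a trial planned at 80% falls to about 61% at s = 20% and about 29% at s = 50%.

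**Step 3: precision, leaving bias aside.** With all 65 participants analysed, SE(d) = √(1/n + d²/(2n)) = √(1/65 + 0.16/130) = √0.01662 = 0.129. The 95% CI is 0.40 ± 1.96 × 0.129, or about 0.15 to 0.65. Dropout would widen it.

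**The case against.** The strongest reply is that this is a usability study. Its aims are feasibility and usability, its primary outcome is the System Usability Scale at T1, and a single arm suits both. Section 6.0 speaks of change from baseline to end of study and nowhere attributes it to MDC-m. All of that stands, and the primary analysis is untouched. It does not rescue the Section 5.0 sentence, which gives the observed change a use that the design cannot support.

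A reader might go further in several ways. The documents do not support these readings.

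- *Later trials will probably be underpowered.* The documents give neither the size nor the direction of change without MDC-m, and do not describe the later trial. With no shared change there is no loss from this source, and if controls worsen the trial is oversized.
- *Regression to the mean inflates the change.* A shift in the group mean would need selection on extreme baseline values. Section 3.0 sets no threshold on any secondary outcome, and the sampling targets are health literacy and age, neither of which is a pre/post outcome.
- *Recruitment around a clinic visit drives the change.* One route does "query the EHR for patients with upcoming clinic appointments who meet the discrete inclusion and exclusion criteria". A second uses a report already "created a report that identifies established patients with diabetes who receive care at the primary care clinics participating in the study", with no appointment required. Enrolment is online and not tied to the visit, so the visit may fall before T0, between T0 and T1, or after T1.
- *A paired effect size overstates the between-arm one through its scale.* The plan does not say which SD it will standardize by. If it is the SD of change, 0.40 becomes 0.40 × √(2(1 − r)) on the raw-score scale: 0.31 at correlation r = 0.7 and 0.25 at r = 0.8. At 100 per arm, power falls to 59% and 43% only if follow-up scores are compared without adjustment. A change-score analysis keeps 80%. Baseline adjustment, with residual SD √(1 − r²), gives about 86% and 84%. Scale alone does not imply an underpowered trial.

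**Conclusion.** The point holds as a risk. The plan assigns an effect-size role to uncontrolled change, and the between-arm effect is not identifiable in a study where everyone receives MDC-m. That much follows from the text and needs no assumption.

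The consequence is conditional. If some of the change would also occur without MDC-m, a later trial sized on the full change is too small, and modest shares matter: under the assumed inputs, a 20% share takes 80% power to about 61%. The bias could also run the other way. Separately, an estimate from 65 people is too imprecise to fix a target difference, even if unbiased. The SDs and the T0–T1 correlation remain useful planning inputs, and the usability conclusions are not affected.

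**What to change.** **Section 5.0.** Replace the stated purpose of the pre/post outcomes with: *to estimate the SDs at T0 and T1, the SD of change and the T0–T1 correlation, with 95% CIs*. Add that the target difference for later trials will be a prespecified meaningful difference, or will come from controlled data, and will not be the change observed here.

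**Section 6.0.** Report each T0–T1 change with a 95% CI and label it as uncontrolled change, not as an effect of MDC-m.

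Splitting the sample by whether a participant had a clinic visit or medication change during the month is not a substitute for a control arm and is not recommended. Those events come after baseline and may themselves result from MDC-m, which is meant to produce more activated patients. They are also not among the outcome data the plan collects.

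**Cost.** Wording in two sections, with no new participants, visits or data. The downside is that the study no longer supplies a ready-made effect size, so the next trial's target difference must be justified in another way.
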